The efficacy and safety of carrimycin treatment in patients with novel coronavirus infectious disease (COVID-19) : A multicenter, randomized, open-controlled study

Study protocol

Version No.:	V5.0			
Version date:	February 20, 2020			
	Beijing YouAn Hospital, Capital Medical			
	University			
	Shenyang Tonglian Group Co., Ltd.			
	Institute of Medicinal Biotechnology, Chinese			
	Academy of Medical Sciences			
	Huangshi Central Hospital			
	Shenyang Pharmaceutical University			
	The First Affiliated Hospital of Chongqing			
Study sites:	University of Medical Science			
	The Second Affiliated Hospital of Harbin			
	Medical University			
	No.2 People's Hospital of Fuyang City			
	The First Affiliated Hospital of Bengbu			
	Medical College			
	Renmin Hospital of Wuhan University			
	The Six People's Hospital of Shenyang			
	Nanyang Central Hospital			
Principal investigators:	Director [name]			

Project Consultant: Academician [name]

Confidentiality

This clinical study protocol is a confidential document for the purpose of this clinical study and shall not be disclosed to anyone other than the investigators involved and members of the institutional review board.

Synopsis

	The efficacy and safety of carrimycin treatment in patients with novel						
Name of study	coronavirus infectious disease (COVID-19): A multicenter,						
	randomized, open-controlled study						
	Evaluate the efficiency and safety of Carrimycin in the patients with						
Study Objectives	2019-nCoV pneumonia, establish the criteria for clinical cure and						
	the early predictive model of COVID-19 progression.						
	A randomized, open, positive-controlled and multi-center clinical						
Study design	study						
Planned sample	500 subjects along a						
size	520 subjects planned.						
	Subjects shall meet all the following criteria before being						
	included:						
	Inclusion criteria						
	(1) Subjects or their legal representatives have signed the informed						
	consent form(ICF); agree not to participate in other clinical						
	studies within 30 days after the last administration from the first						
	administration of the study drug.						
	(2) Subjects are aged \geq 18 and \leq 75;						
	(3) Meet the diagnostic criteria for 2019-nCoV pneumonia (V5.0);						
Inclusion/exclusion	(4) SOFA score: 1 ~ 13 points.						
criteria	(5) A retreated patient or the relapsed patient meets any of the						
	following criteria:						

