	1 Have fever again or aggravated clinical symptoms; 2						
	2019nCOVRNA in the throat swabs converts from negative to						
	positive; ③ The clinical symptoms don't improve or						
	2019nCOVRNA continues to be positive; ④ The chest CT						
	shows pneumonia or fibrosis progression.						
	Clinical stratification:						
	1. Mild type: clinical symptoms mild or asymptomatic, no						

pneumonia performance in CT, but positive 2019-nCoV in throat
swabs or gargle.
2. Ordinary type: fever, respiratory symptoms, etc., pneumonia
performance visible in CT.
3. Severe type: meeting any of the following criteria:
(1) Respiratory distress, RR≥30 times/min;
(2) Finger oxygen saturation ≤93% in rest state;
(3) Arterial partial pressure of oxygen (PaO2)/concentration of
oxygen inhalation (FiO2)≤300mmHg (1mmHg=0.133kPa).
4. Critical type: meeting any of the following criteria:
(1) Respiratory failure occurs and mechanical ventilation is
required;
(2) Patients go into shock;
(3) ICU is needed for other organ failure.
Exclusion criteria
(1) Other viral pneumonia
(2) Patients who have received tumor immunotherapy (such as
PD-1/L1, CTLA4, etc.) in the past 1 month, and inflammatory
factor modulators such as Ulinastatin;
(3) Patients who have taken anti-bacterial drugs such as macrolide
in the past 1 week;
(4) Patients who have received organ transplantation or surgery
planning in the past 6 months;
(5) Patients who can't take food or drugs due to coma or intestinal
obstruction;
(6) Patients who have severe underlying diseases that affects
survival, including uncontrolled malignant tumor with multiple
metastases that cannot be resected, blood diseases, dyscrasia,
active bleeding, severe malnutrition, etc.
(7) Women subjects that are pregnant or lactating, or subjects
(including male subjects) having a pregnancy plan (including

		plans for sperm donation or egg donation), or subjects that may
		fail to take effective contraceptive measures within the next 6
		months;
		(8) Patients with allergic constitution, or patients allergic to
		macrolides and lopinavir/ritonavir tablets;
		(9) Patients with contraindications to lopinavir/ritonavir tablets who
		plan or are using drugs that interact with the drug (including:
		drugs that are highly dependent on CYP3A clearance and
		whose elevated plasma concentrations can be associated with
		severe and/or life-threatening events [with a narrow therapeutic
		index], CYP3A inducer [see instruction for details]) and cannot

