		stop using or use other drugs instead;
		(10)Patients whose ALT/AST levels are 5 times higher than the
		normal upper limit and total bilirubin is 3 times higher than the
		upper limit of normal, or patients with child-Pugh grade C
		cirrhosis.
		(11)ECLS (ECMO, ECCO2R, RRT)
		(12)Critical patients with expected life \leq 48 hours
		(13)Patients who have participated in any other clinical study within
		1 month;
		(14) The investigators conclude that the patients not suitable for the
		study.
		The trail group and the control group were randomized according to
		1: 1.
		(1) Trial group: basic treatment + Carrimycin
Trial drugs a	nd	Mild type: 0.4g of Carrimycin tablets, p.o. after meal once a day for 7
medication		consecutive days, followed up for observation after the end of
methods		treatment.
		Ordinary type: 0.4g of Carrimycin tablets, p.o. after meal once a day
		for 10 days, followed up for observation after the end of treatment.
		Severe and critical: 0.4g of Carrimycin tablets, p.o. after meal once
		a day for 14 consecutive days. If oral administration is not possible,

	the drug should be administered through a nasal feeding tube.
	For the combination drugs of basic treatment according to the
	Diagnosis and Treatment Program for 2019-nCoV (V5.0,Chinese)
	 (2) Control group: any of basic treatment + lopinavir/ritonavir tablets or Arbidol or chloroquine phosphate: Mild and ordinary type: 400mg/100mg, bid of lopinavir/ritonavir
	tablets each time: or 500mg bid of chloroguine phosphate: or 200mg
	tid of Arbidel for 7 consecutive days, followed up for absorvation
	after the end of treatment.
	Severe and critical type: 400mg/100mg, bid of lopinavir/ritonavir
	tablets each time; or 500mg bid of chloroquine phosphate; or 200mg
	tid of Arbidol for 10 consecutive days, followed up for observation
	after the end of treatment.
	For the combination drugs of basic treatment according to the
	Diagnosis and Treatment Program for 2019-nCoV (V5.0,Chinese)
	Permitted therapy combination and/or drug combination:
	Clinical treatment schemes other than antiviral therapy in the
	Diagnosis and Treatment Program for 2019-nCoV (V5.0,Chinese) are permitted.
	Acetaminophen (paracetamol), diclofenac sodium suppositories,
	lyripine (lysisin aspirin) antipyretics are prohibited.
Therapy/drug	
combination	Prohibited therapy combination and/or drug combination:
	No other antiviral drugs or antibiotics are allowed during the trial

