	(except retreated or relapsed patients or in severe and critical type
	cases).
	Keep a detailed record of the dugs combination, especially the
	glucocorticoids.
Observation and its i	Screening period: -2 days~ 0 day;
Observation period	Treatment period: 7-14 days;

	Follow-up observation period: follow up to 30 days after the first							
	administration.							
	Primary efficiency indicators							
	(1) Fever to normal time (day)							
	(2) Pulmonary inflammation resolution time (HRCT) (day)							
	(3) Negative conversion (%) of 2019-nCOVRNA in gargle (throat							
	swabs) at the end of treatment							
	Secondary efficiency indicators							
	(1) Negative conversion ratio of 2019-nCOVRNA in gargle (throat							
	swabs), urine and stool on Day 1, 3, 5 and 14 after							
	administration;							
	(2) Progress rate of 2019-nCoV pneumonia							
	(3) Changes in immune-related indicators (lymphocyte count,							
	lymphocyte percentage, counts and percentages of CD4 and							
	CD8, and inflammatory cytokines) from baseline on Day 1, 3, 5							
	and 7-10 after administration.							
Effectiveness	(4) Changes in SOFA score from baseline on Day 1, 3, 5 and 7-10							
indicators	after administration;							
	(5) Changes in white blood cell count from baseline on Day 1, 3, 5							
	and 7-10 after administration;							
	 (6) Changes in PCT and C-reactive protein from baseline on Day 1, 3 5 and 7-10 after administration: 							
	(7) Changes in CT features from baseline on Day 7-10 and 14 after							
	administration;							
	(8) Length of stay in hospital and mortality rate.							
	There are currently criteria for release from clinical isolation and							
	discharge on 2019-nCoV pneumonia (V5.0,Chinese), and there is							
	no "gold standard" for clinical cure, and it is difficult to obtain the							
	basis for pulmonary diagnosis. Therefore, the following criteria are							
	currently used clinically (empirical evidence, lack of scientific							
	evidence) and it is not known whether there is a chronic infection or							

	virus carrying. Therefore, the following criteria are used for the					
	clinical assessment in this project:					
	Criteria for clinical cure:					
	1) The clinical symptoms disappear and the quality of life is					
	normal.					
	2) Lung CT/HRCT is normal.					
	3) T lymphocyte function and count return to normal.					
	4) Negative 2019-nCOV in secretions (gargle, urine and stool)					
	Clinical chronic or complications:					

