	1) Gastrointestinal and respiratory symptoms completely					
	disappear, the quality of life is lowered (anxiety, insomnia and					
	other mental disorders) or the lung CT/HRCT lesions exist, or					
	lung fibrosis is formed.					
	2) Or laboratory abnormalities (blood routine, T lymphocyte count					
	or function).					
	3) Negative 2019-nCOV in secretions (gargle, urine and stool)					
	(1) AE, SAE.					
	(2) Vital signs: breath, blood pressure, heart rate, body					
	temperature.					
	(3) Laboratory examination: blood routine (WBC, RBC, Hb, HCT, PLT,					
Safety indicators	LY and LY%), urine routine (WBC, RBC, Pro), blood					
	biochemical examinations (ALT, AST, TBIL, ALP, GGT, Cr, BUN,					
	Glu) and coagulation function (PT, APTT, TT, FIB).					
	(4) Routine ECG: heart rate, Q-Td, ST segment and T wave					
	changes.					
	(1) General principle					
	1) Description of statistics					
	The primary indicators collected in this study are described with					
Statistical analysis	statistical method. Quantitative indicators are described by means of					
	mean, standard deviation, median, quartile, maximum, minimum					
	and the like; qualitative indicators are described by frequency,					
	percentage and the relationship.					

2) Statistical test
Unless otherwise specified, the statistical significance level is
0.05 by two-sided test (one-sided 0.025) and the 95% confidence
interval shall be provided for the estimation of inter-group variance
parameters.
3)Random grouping: The hierarchical random grouping method
is adopted
(2) Characteristics of cases
1) Subject distribution
1 The population and the number of enrolled and completed
cases in each center are listed, and three analysis data sets
(FAS, PPS, SS) are determined.
② A detailed list of the data set categories is made.
${}^{\textcircled{3}}$ The number and ratio of subjects who are randomly
enrolled, complete the trial, and withdraw from the trial early
and the reasons are calculated.
④ The subject distribution flow chart is plotted.
2) General information and baseline characteristics
The demographic information, previous medication history and
history of other diseases of the patients are described with statistical
method. General information and baseline characteristics are
described based on FAS.
(3) Analysis of drug exposure and drug combination
Analysis based on SS.
1) Drug exposure, dose intensity and exposure time of each
group are calculated.

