2) The drug combination is coded by WHO ATC and
summarized according to the ATC secondary classification
and PT. The number and ratio of cases are calculated.

(4) Efficiency analysis

Analysis based on FAS and PPS.

The primary effective indicator are:(1) Fever to normal time (day),(2)Pulmonary inflammation resolution time (HRCT) (day),(3)Negative conversion (%) of 2019-nCOVRNA in gargle (throat swabs) at the end of treatment on Days 7-10 after administration. The statistical significance level is set to one-sided 0.025. The two-sided 95% confidence interval (95%CI) are confidence calculated. The interval is estimated bv Miettinen-Nurminen.

The secondary efficiency indicators include negative conversion ratio of 2019-nCOVRNA from samples, immune-related indicators (lymphocyte count, lymphocyte percentage, counts and percentages of CD4 and CD8), SOFA score, white blood cell count, C-reactive protein, pulmonary imaging improvement indicators and complete antipyresis time on Day 1, 3, 5 and 14 after administration. In-hospital time, clinical cure ration and mortality are also analysed. The secondary efficiency indicators are subject to descriptive statistical analysis according to the data type.

(5) Safety analysis

SS data sets are used for safety analysis.

- 1) Adverse events are coded according to the MedDRA.
- 2) The occurrence of adverse events/reactions, serious adverse events/reactions and adverse events/reactions resulting in drop out is summarized and analyzed in the form of a frequency table (number of cases, case, and incidence).
- 3) The occurrence of varying severity orders of adverse events/reactions, serious adverse events/reactions and adverse events/reactions resulting in drop out is subject to descriptive statistical analysis in the form of a frequency

	Screenin g period		Med	dication pe	follow-up observation period		Forte		
Study stage	Day -2 ~ day 0 (baselin e)	Day 1	Day 3	Day 7	Day 10	Day 14	Day 14 ±1 days	Day 28 ± 2 days	Early withdrawal
Visit	1	2	3	4	5	6	7	8	
Informed consent form	×								
Demographic information	×								
Medical data	×	×	×	×	×	×	×	×	
Vital signs	×	×	×	×	×	×	×	×	×
SOFA score	×		×	×	×	×		×	
Physical examination	×	×	×	×	×	×	×	×	×
Review of inclusion/excl usion criteria	×	×							
Blood routine ³	×		×	×	×	×	×	×	×
Urine routine ⁴	×		×	×	×	×	×	×	×
Blood biochemistry ⁵	×		×	×	×	×	×	×	×
Coagulation function ⁶	×		×	×	×	×			×
T cell subset and cytokines 7	×		×	×	×	×	×	×	×
C-reactive protein	×		×	×	×	×			×

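### Randomisation is described as stratified, but the one primary interval named makes no stated use of strata: valid but conservative if followed as written, and suited only to the proportion endpoint

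*Protocol*

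**What the plan says.** All references are to the protocol's Synopsis.

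- **Randomisation.** Allocation is 1:1 (Trial drugs and medication methods). Statistical analysis (1), General principle, item 3, reads "Random grouping: The hierarchical random grouping method" and says that this method is adopted. No stratification factor is named there.
- **Clinical types.** Under the inclusion criteria, a list headed "Clinical stratification" defines mild, ordinary, severe and critical disease. It is the only stratification that the document defines. No sentence links it to the randomisation.
- **Sample size.** "520 subjects planned"; the same cell also carries a fragment that reads 500. No power, rates or effect size accompany it.
- **Primary indicators.** Two are times in days, to normal temperature and to resolution of lung inflammation on HRCT. One is a proportion, negative conversion of viral RNA at the end of treatment.
- **Primary analysis.** In Statistical analysis (4): "The statistical significance level is set to one-sided 0.025", with a two-sided 95% confidence interval, and then "The interval is estimated bv Miettinen-Nurminen". Neither stratum, clinical type nor centre is mentioned, and no other method for the primary indicators is named.

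**The concern.** Stratified allocation balances the arms within strata, so differences between strata drop out of the treatment contrast. A standard error computed from the pooled arms still contains them. The pooled interval is then wider than the design warrants, and the test rejects less often than its nominal 0.025 under the null. What is at stake is efficiency that the design has already paid for, not validity.

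The document gives reason to expect the clinical types to differ on the primary indicators. Mild cases have no pneumonia on CT and may be asymptomatic, while ordinary cases include fever and visible pneumonia. Conversion is assessed at the end of treatment, and treatment length varies by type (7, 10 or 14 days in the trial arm, 7 or 10 in the control arm).

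A second problem sits at the same sentence. Miettinen-Nurminen is an interval for a difference or ratio of proportions. It cannot be applied to "1) Fever to normal time (day" or to the lung-inflammation time, so those two primary indicators have no method that fits them.

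**Working it through.** **No figure to reproduce.** The planned size cannot be reproduced because the inputs to it are not given.

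**Inputs from the protocol:** 520 patients, 1:1, so n = 260 per arm; one-sided 0.025 (z = 1.96); four clinical types.

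**Assumptions:** clinical type is the randomisation stratum; arms are balanced within strata; the stratum shares w and control conversion rates p are those in the table; the true gain is d = 0.12 in every stratum.

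**Formulas.** Let P0 and P1 be the overall rates (the sums of w·p) and p0, p1 the stratum rates.

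- Variance used by the pooled interval: Vu = [P0(1−P0) + P1(1−P1)] / n
- Variance under stratified allocation: Vs = Σ w[p0(1−p0) + p1(1−p1)] / n
- Relative width: √(Vu/Vs)
- Power, pooled: Φ[(d − 1.96√Vu)/√Vs]; stratified: Φ[d/√Vs − 1.96]
- Actual one-sided size of the pooled test: 1 − Φ(1.96/√r), where r is the ratio of within-stratum to total variance under the null

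**One case in full** (shares 20/50/20/10%, control rates 85/65/40/20%):

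- Control: P0 = 0.170 + 0.325 + 0.080 + 0.020 = 0.595, so the total variance is 0.595 × 0.405 = 0.2410. Within strata it is 0.0255 + 0.1138 + 0.0480 + 0.0160 = 0.2033.
- Null: r = 0.2033/0.2410 = 0.843, so size = 1 − Φ(1.96/0.918) = 1 − Φ(2.134) = 0.016.
- Trial arm (97/77/52/32%): P1 = 0.715, total 0.2038, within strata 0.1661.
- Vu = (0.2410 + 0.2038)/260 = 0.001711, root 0.0414, half-width 0.0811.
- Vs = (0.2033 + 0.1661)/260 = 0.001420, root 0.0377, half-width 0.0739.
- Relative width 0.0811/0.0739 = 1.097, so 9.7% wider.
- Power, pooled: Φ[(0.12 − 0.0811)/0.0377] = 84.9%; stratified: Φ[0.12/0.0377 − 1.96] = 88.9%.

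**Range.** Widening is from the formulas. Size and power are from simulated trials of 520 patients (200,000 for size, 100,000 for power), using the score test at zero difference with the Miettinen-Nurminen N/(N−1) factor. The stratified version weights by stratum size.

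| Control rates, mild to critical | Shares | Pooled interval wider by | One-sided size, pooled / stratified | Power, pooled / stratified |
|---|---|---|---|---|
| 60% in all | equal | 0% | 0.026 / 0.026 | 82.5% / 82.5% |
| 65/60/55/50% | 20/50/20/10% | 0.4% | 0.024 / 0.025 | 82.0% / 82.2% |
| 75/65/50/40% | 20/50/20/10% | 2.8% | 0.023 / 0.025 | 84.2% / 85.6% |
| 85/65/40/20% | 20/50/20/10% | 9.7% | 0.016 / 0.024 | 84.4% / 88.8% |
| 85/65/40/20% | equal | 15.7% | 0.012 / 0.025 | 82.8% / 89.7% |

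With 500 patients the formulas give nearly the same losses, from 0 to 7.0 points.

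**An intermediate case under the null.** Shares 10/60/20/10% with rates 90/75/50/30% give an overall rate of 0.67, total variance 0.67 × 0.33 = 0.2211, within-stratum variance 0.009 + 0.1125 + 0.050 + 0.021 = 0.1925, ratio 0.871 and size about 0.018. The excess variance corresponds to (1 − 0.871) × 520, or about 67 patients. A uniform 12-point gain is impossible from 90%, so no power is given for this case.

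**The case against.** The strongest reply is that the protocol never says unstratified. Miettinen-Nurminen has a stratified form, the text is silent on which is meant, and such detail is commonly left to the SAP, which is not at hand. The randomisation factors are not named either. In a multicentre trial the factor could be centre, and the mild-to-critical calculation would then not apply. Much of this stands: both the unstratified reading and clinical type as the stratum are inferences. What does not fall away is that the protocol names a method beside its alpha level and does not say that the strata used for allocation enter. Followed as written, that is the ordinary two-sample interval.

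A reader might infer four stronger things that the documents do not support:

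- **That the interval is invalid or the error rate inflated.** The departure is conservative: under the null the pooled size falls below 0.025 as the strata diverge.
- **That the loss is certainly substantial.** It depends on rates that the protocol does not give, and it is negligible to small unless the strata differ widely.
- **That the two time endpoints lose a known amount of power to an unstratified log-rank test.** The protocol names no log-rank test. Mild cases, with no pneumonia on CT, also have no inflammation to resolve. The defect for the times is that the named method does not fit them.
- **That retreated or relapsed status should also be adjusted for as a covariate.** A stratified Miettinen-Nurminen difference takes strata, not additional covariates.

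**Conclusion.** The point holds as a matter of precision. The protocol describes stratified randomisation without naming the factors, and its only stated primary method makes no use of strata. If that method is applied as written and conversion differs by stratum, the result for the proportion is conservative. The cost lies between nothing and about 1.4 power points for no to moderate differences between strata, and is about 4 to 7 points for wide ones. These figures assume clinical type as the stratum, balance within strata, a constant 12-point gain and the stratum rates and shares in the table; none of these comes from the protocol. Independently of any rates, the named interval does not fit two of the three primary indicators.

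**What to change.** In Statistical analysis (4):

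1. Name the factors actually used in the randomisation. Clinical type is the only stratification that the document defines; if it was the factor, say so, and if centre or something else was used, name that.
2. State that negative conversion is compared by a Miettinen-Nurminen difference stratified by those factors and weighted by stratum size, with a rule set in advance for merging sparse strata.
3. State that the two times are analysed by a stratified log-rank test or stratified Cox model on the same factors.

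The cost is a few sentences in the protocol, carried into the SAP, with no new data and slightly more analysis work. The one practical drawback is that some strata may be sparse, which the merging rule handles. The change should be made before outcome data by arm are seen.

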2019-nCOVRNA in throat swabs, urine and stool	×	×	×	×	×	×	×	×	×
Chest imaging (CT)	×			×	×	×	×	×	×
12-lead ECG	×			×	×	×			×
Pregnancy test ⁸	×							×	×
Enrollment		×							
Administration		×	×	×	×	×			

Flow chart of clinical trial

	Screenin g period		Meo	dication p	follow-up observation period				
Study stage	Day -2 ~ day 0 (baselin e)	Day 1	Day 3	Day 7	Day 10	Day 14	Day 14 ±1 days	Day 28 ± 2 days	Early withdrawal
Visit	1	2	3	4	5	6	7	8	
Record of clinical treatment scheme	×	×	×	×	×	×	×	×	×
Trial drug dispensing		×	×	×	×	×			
Trial drug recovery		×	×	×	×	×			×
Combination therapy	×	×	×	×	×	×	×		
Reserve throat swabs	×	×	×	×	×	×	×	×	×
Reserve blood specimens (serum, plasma and cells)	×	×	×	×	×	×	×	×	×
Reserve urine and stool	×	×	×	×	×	×	×	×	×
Adverse event	×	×	×	×	×	×	×	×	×

Notes:

1. Visit 1 (screening period) and visit 2 (baseline) may be on the same day, and Day 0 is the first day of administration;

2. To withdraw from the trial in advance, it is necessary to complete the last visit items; in case of AE at the end of the trial, follow-up should be conducted according to the "AE" requirements of the protocol;

- 3. Blood routine examinations: including WBC, RBC, Hb, HCT, PLT, LY, LY%;
- 4. Urine routine examinations: including WBC, RBC, Pro;
- 5. Blood biochemical examinations: including ALT, AST, TBIL, ALP, GGT, Cr, BUN, Glu;
- 6. Coagulation function: including PT, APTT, TT, FIB;
- 7. T cell subset: counts and percentages of CD4+ and CD8+;

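### Visits 6 and 7 put two CT scans within a day of each other at Day 14, and the next scheduled scan is Day 28, so later times on the primary CT endpoint are read about two weeks wide

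*Protocol*

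**What the plan says.** All references are to the Protocol.

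- Flow chart of clinical trial, header: Visit 6 closes the medication period, and Visits 7 and 8 form the follow-up period. Their days are "Day 14 Day 14 ±1 days Day 28 ± 2 days". The numbering "Visit 1 2 3 4 5 6 7 8" leaves no visit between 7 and 8.
- Flow chart, row "Chest imaging (CT": CT is marked at Visit 1, at Visits 4 to 8 and at early withdrawal. It is therefore due at both Visit 6 and Visit 7.
- RNA, blood and urine routine, biochemistry, T-cell tests, vital signs and physical examination are also marked at both. SOFA, coagulation, C-reactive protein and ECG are marked at Visit 6 but not at Visit 7.
- Synopsis, Effectiveness indicators: the second primary endpoint is "Pulmonary inflammation resolution time (HRCT) (day", a time in days.
- Synopsis, Observation period: "Treatment period: 7-14 days", then "Follow-up observation period: follow up to 30 days after the first" administration.
- Synopsis, Trial drugs and medication methods: only severe and critical patients in the trial group have a 14-day course. All other courses last 7 or 10 days.
- The flow-chart notes shown do not tie Visit 6 or Visit 7 to a particular course length. Note 1 makes Day 0 the first day of dosing, whereas the administration row begins at Day 1.

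**The concern.** A time-to-resolution endpoint is only as fine as the scans that detect it. As the chart is written, two of the five scheduled post-baseline scans fall within a day of each other at Day 14, and the second adds almost nothing to the first. Between there and Day 28 nothing is scheduled. Any patient whose lungs clear in that stretch is first seen as clear about four weeks after the first dose, whether clearance came on Day 17 or Day 26.

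At stake is how well the trial can describe the endpoint in days. If the typical patient clears in weeks three or four, the reported medians, and any difference between arms in days, will largely reflect the visit calendar. The scan that could prevent this is already in the schedule, at a day where it is of little use.

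**Working it through.** The plan states no expected resolution time, so there is no figure of its own to reproduce. The first three steps are date arithmetic. Steps 4 to 6 are illustrations on assumed distributions.

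**1. Spacing of the visits.**
- Visit 6 to Visit 7: 13 − 14 = −1 to 15 − 14 = +1 day.
- Visit 7 to Visit 8: nominally 28 − 14 = 14 days; shortest 26 − 15 = 11; longest 30 − 13 = 17.
- Visit 6 to Visit 8: 26 − 14 = 12 to 30 − 14 = 16 days.

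**2. Could the follow-up days run from the end of treatment?** With courses of 7, 10 and 14 days, Visit 7 would fall on Day 21, 24 or 28, and Visit 8 on Day 35, 38 or 42. The Synopsis ends follow-up 30 days after the first dose, which equals Day 28 + 2 counted from that dose. The documents therefore do not support this reading.

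**3. What the grid shows.** The nominal post-baseline CT days are 7, 10, 14 and 28. A median is first observed at the first scan on or after it.

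| True medians in the two arms (days) | Seen on 7/10/14/28 | Seen on 7/10/14/21/28 |
|---|---|---|
| 15 and 20 | 28 and 28 | 21 and 21 |
| 16 and 27 | 28 and 28 | 21 and 28 |
| 18 and 24 | 28 and 28 | 21 and 28 |

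**4. Share of resolutions in the gap.** Share = [F(28) − F(14)] / F(28), where F is the distribution of resolution time. For the lognormal, F(t) = Φ(ln(t/m)/0.5), with median m. For the exponential, F(t) = 1 − 0.5^(t/m).

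| Assumed median m (days) | Lognormal, sigma 0.5 | Exponential |
|---|---|---|
| 7 | (0.997 − 0.917)/0.997 = 8% | (0.938 − 0.750)/0.938 = 20% |
| 10 | (0.980 − 0.750)/0.980 = 24% | (0.856 − 0.621)/0.856 = 27% |
| 14 | (0.917 − 0.500)/0.917 = 45% | (0.750 − 0.500)/0.750 = 33% |
| 18 | (0.812 − 0.308)/0.812 = 62% | (0.660 − 0.417)/0.660 = 37% |
| 21 | (0.717 − 0.209)/0.717 = 71% | (0.603 − 0.370)/0.603 = 39% |

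As a share of all patients, F(28) − F(14), the exponential gives 19% to 25% over these medians.

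**5. Delay from true to observed resolution, for patients who resolve between Day 14 and Day 28.** For an exponential with rate λ = ln 2/m and a gap of width w, the mean delay is w − [1/λ − w/(e^(λw) − 1)]. With m = 14:
- w = 14: 14 − [20.20 − 14/(2 − 1)] = 7.8 days.
- w = 7: 7 − [20.20 − 7/(1.414 − 1)] = 3.7 days.

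Over medians of 7 to 21 days the range is 7.5 to 8.6 days with the present grid and 3.6 to 3.9 days with a Day 21 scan.

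**6. Power.** I simulated a log-rank test with 260 patients per arm (520 / 2), exponential medians of 21 and 16.5 days and two-sided 0.05. Power was about 0.60 with either grid, and the extra time point moved it by about one percentage point or less.

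**The case against.** The strongest reply is that the double Day 14 is deliberate. Visit 6 carries drug administration and dispensing, and only trial-group severe and critical patients are still on a course that long: "a day for 14 consecutive days. If oral administration is not possible". Everyone else could be meant to use Visit 7 as their Day 14 visit. This is a sensible guess at the intent, but the chart does not say it. It would also leave the repeated scan for the 14-day patients and the Day 14 to 28 gap for all. What stands is its bearing on cost: under that intent, a Day 21 visit is an addition for patients on shorter courses.

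A second reply is that dating rules and interval-censored methods belong in an SAP, which is not shown. That is fair, and their absence here is not a fault. Such methods would report the uncertainty honestly, but they cannot narrow an interval in which no scan was taken.

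Several stronger readings are tempting and should not be drawn:

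- That times can only be 7, 10, 14 or 28 days, or that every Day 15 clearance is missed. The windows allow 13, 15 and 26 to 30, a Visit 7 held on Day 15 can record a Day 15 clearance, and early-withdrawal or unscheduled scans may fall in the gap.
- That Visit 7 is a full copy of Visit 6. Four assessments are marked at Visit 6 only.
- That the gap hides RNA relapse and so harms an endpoint. Relapse after treatment is not a listed efficacy measure; the primary RNA endpoint is at end of treatment, and the secondary RNA times stop at Day 14.
- That Visit 7 precedes the end of a 14-day course, or that such patients have only one off-treatment visit. Counting from Day 0, the course ends on Day 13; counting from Day 1, on Day 14. The protocol does not settle which applies.
- That most resolutions fall in the gap. This needs long assumed medians; with lognormal medians of 7 and 10 days the share is 8% and 24%.

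**Conclusion.** The point holds as a question of measurement precision. On the schedule as written, CT is marked twice within a day at Day 14 and is next due at Day 28 ±2, so a resolution after about Day 15 is first seen at Day 26 to 30. The gap itself (14 days nominal, 11 to 17 with windows) needs no assumption. Its practical weight does: between about 8% and 71% of resolutions seen by Day 28 are affected under the lognormal medians tried, and the protocol gives no basis for choosing among them.

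A reader might infer that the comparison between arms is biased or underpowered. The material does not support that: the same grid applies to both arms, and simulated power hardly moves. The loss is in the stated days and in any difference expressed in days. This makes it a worthwhile, inexpensive improvement and not a defect that undermines the trial.

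**What to change.** 1. Keep one Day 14 assessment (Visit 6) for every patient, and re-time Visit 7 to about Day 21 ±1 with the assessments it already marks. Change the heading in both parts of the flow chart.
2. Add a note that the Day 14 assessments, but not drug administration or dispensing, apply to all patients whatever their course length.
3. State one day origin, Day 0 or Day 1, and use it throughout.

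The longest nominal interval between post-baseline scans then falls from 14 to 7 days. With windows, Day 14 to Visit 7 is 6 to 8 days, and Visit 7 to Visit 8 is 26 − 22 = 4 to 30 − 20 = 10 days. The Day 14 time points for the secondary CT and RNA measures are kept. Day 21 is chosen for even spacing; another day near the middle of the gap would do much the same.

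Cost: against the chart as written, no visit, scan or sample is added, but discharged patients must return around Day 21. If Visit 6 was meant only for 14-day courses, patients on 7- or 10-day courses gain one visit and scan relative to that intention, together with the SOFA, coagulation, C-reactive protein and ECG marked at Visit 6. The sponsor should confirm the intent before making the change. No gain in power should be claimed for it.
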